Our **long-term goal** is to develop interventions to increase perceived self-efficacy (PSE), perception of ability, for CRF self-management as a means of improving functional status and quality of life for persons with NSCLC.²⁵ Our **objective** in this application is to determine the efficacy, optimal timing of initiation, and sustainability of our 6-wk home-based exercise intervention. The **significance** of this study is that it targets two of the most troublesome unmet needs, fatigue and lack of exercise, in an understudied, vulnerable population with the potential to **transform** the current standard of care by providing a rehabilitative exercise intervention after surgery. The proposed research advances the field by providing both an intervention for CRF self-management and evidence for its optimal initiation and sustainability, which currently does not exist for the post-thoracotomy NSCLC population. Our exercise intervention is guided by a theoretical approach (tested by the PI) incorporating self-efficacy theory to strengthen a person's ability to manage their CRF and walking ability.^{17,26} The exercise intervention is **innovative** in its timing and approach in providing self-paced exercise to a vulnerable post-surgical NSCLC population upon discharge from the hospital. The Nintendo's Wii Fit Plus is used to provide light-intensity, virtual reality walking and balance exercise that departs from the status quo and transcends barriers to exercise, as demonstrated by our R21 RCT retention and adherence outcomes.

This study employs a three-arm RCT for persons undergoing NSCLC surgery with participants being randomly assigned to an immediate (post-hospital discharge) exercise intervention group, a wait-list control group (6 wks usual care [wks 1-6] and 6 wks exercise [wks 7-12]), or a 6 wk attention control group (wks 1-6).

Protocol Version 4.0 (7/19/2023). UNMC IRB 560-18 EP. Contact PI: [name] [name], RN.

Primary Outcome: Cancer-Related Fatigue (Severity and Fatigability).

Secondary Outcomes: Severity of Other Symptoms; PSE for CRF Self-Management, Walking, and Balance; Functional Performance; and Quality of Life (QOL).

Aim 1: Determine efficacy of three groups by comparing: 1) immediate exercise intervention group; 2) a wait-list control group; 3) an attention control group by age. Hypothesis 1: The exercise intervention group will outperform wait-list and attention control on all primary and secondary outcomes at wk 6 for all ages.

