Aim 2: Determine efficacy of initiating the exercise intervention 6 wks post-discharge and compare results with the immediate intervention group by age. Hypothesis 2: The immediate exercise intervention group will improve for all ages at a greater rate and magnitude than the wait-list group for all outcomes.

Aim 3: Determine the immediate exercise intervention's sustainability by analyzing a) rates of extension, adherence, and retention; b) acceptability; and c) efficacy of primary and secondary outcomes. Hypothesis 3: The exercise intervention will be acceptable with >50% extending at wk 6 and >70% adherence and retention at wk 12, with improved primary and secondary outcomes at wk 12.

IMPACT: Our results will provide a novel, practical, portable, low-cost, and enjoyable exercise intervention with important information on its optimal timing and sustainability to fill the gap regarding approaches that are applicable to nearly all post-thoracotomy lung cancer patients for reducing CRF severity and fatigability.^{20,22,27-32}

Section 2.0 Introduction

Significance

2A) OVERALL SCIENTIFIC PREMISE

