Fatigability (fatigue with activity, indicator of functional capacity) was measured by the 6-min walk test (6MWT) pre-surgery and post-study, by assessing fatigue reported during the 6MWT and distance walked in 6 mins.¹¹⁰ The IG's wk 6, post-study fatigability decreased from pre-surgery while the UCG's *increased*. IG's fatigue during 6MWT (0-10, 10= most severe) decreased from pre-surgery (M=2.0, SD 1.7) to post-intervention (M=0.4, SD 0.8) while their distance walked increased by a mean of 15% (SD 15). Conversely, the UCG's fatigability *increased* as their 6MWT fatigue increased from pre-surgery (M=1.5, SD 1.8) to post 6 wks (M=3.1, SD 1.5) while their distance walked decreased by a mean of 21% (SD 19). The difference between the IG and UCGs' fatigue during the post-study 6MWT was significant [t (50.9) = -9.3, p<.001; 95% CI -3.3 to -2.1; d = 1.8] as was % change in distance walked post-study vs. pre-surgery 6MWT [t (70) = 9.0, p < .001; 95% CI 28 to 44; d = 1.9].

[figure not shown]

Figure 7. Physical and Mental Health Component Summary SF-36 (60 = Greater Mental/Physical Health)

15 Other symptoms' (not including fatigue) frequency, severity, and interference levels were measured using the M.D. Anderson Symptom Inventory.¹¹¹ Fig 6 shows number, severity, and interference from pre-surgery to wk 6, post-study for IG and UCGs. **Mean # symptoms** reported by the IG decreased from 8.4 (SD 2.4) post-surgery to 4.6 (SD 3.2) at wk 6 post-study, while the UCG reported a mean of 6.6 (SD 3.3) post-surgery and increased to 7.4 (SD 3.3) at wk 6, post-study, a significant difference between groups at wk 6 [t (70) = -3.7; p<.001; 95% CI -4.4 to -1.3; d = 0.9]. Likewise, **mean symptom severity** of the IG was 4.7 (SD 1.5) post-surgery and decreased to 2.1 (SD 1.0) at wk 6, while the UCG started equivalent to the IG post-surgery at a mean severity of 4.9 (SD 1.6) and only reduced to a mean level of 3.8 (SD 1.5) by wk 6, a significant difference between groups at wk 6 [t (61.2) = -5.6; p<.001; 95% CI -2.3 to -1.1; d = 1.1].

For **mean symptom interference**, the IG reported post-surgery mean interference of 3.3 (SD 2.1) decreasing to a level of 0.5 (SD 0.8) at wk 6, while the UCG reported a post-surgery mean interference of 4.5 (SD 2.8) and improved to an interference level of 2.9 (SD 2.3) at wk 6, a significant difference between groups at wk 6 [t (41.8) = -6.0; p< .001; 95% CI -3.2 to -1.6; d = 1.1].

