Functional Performance was measured using the Medical Outcomes Short-Form-36 (SF-36)¹¹² pre-/post-surgery and after wks 3 & 6. SF-36 uses norm-based scoring with physical and mental health components of the SF-36 scored to have the same mean (50) and SD (10) in the general U.S. population, with component scores ranging from 20 to 70. The Mental Health component of the IG (Fig 7) consistently improved from a mean pre-surgery level of 48.2 to 57.5 at wk 6 (exceeding national norm of 50). Conversely, the UCG's mean Mental Health component scores *dropped* after surgery and stayed relatively flat for wks 3 & 6 (47.4 and 47 respectively). Physical Health component scores dropped for both groups post-surgery, with IG's improving from post-surgery 30.2 to a wk 6 of 45.2. The UCG improved at a much slower rate, starting at post-surgery level of 32.7 and improving to 38.8 at wk 6 post-study.

[figure not shown]

Figure 6. Other Symptom Mean Scores (Number, Severity, Interference) (0-10. 10 = Most Severe and Most Interference)

Implications of Preliminary Work. Results justify efficacy testing with a larger sample, attention control group, and focus on optimal timing and sustainability of the exercise intervention. The proposed intervention retains all pilot components, incorporating participant feedback to add exercise flexibility with/without the Wii after achieving 10 mins/day of continuous walking for 5 days/wk.

Section 3.0 Eligibility Criteria

The research proposed for this application is a randomized controlled trial (RCT) to determine the efficacy, optimal timing, and sustainability of an innovative home-based exercise intervention for post-surgical non-small cell lung cancer (NSCLC) patients after discharge from the hospital. This exercise intervention is designed to enhance perceived self-efficacy (PSE) for cancer-related fatigue (CRF) self-management to improve CRF severity and fatigability (fatigue associated with activity, an indicator of functional capacity) to augment the rehabilitation of persons of all ages with NSCLC after surgery.

No special vulnerable populations will be studied.

Eligibility. Based on results of our R21 RCT, we will use criteria shown for participation in this study:

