5C2) Study Procedures. IIG participants will have baseline data collected by the nurse recruiter. Following principles of transitional care,¹²⁴ the exercise nurse intervener will engage the participant using protocol in Appendix A4 in the hospital post-surgery to review the exercise intervention and teach PSE-enhancing CRF self-management education (Appendix A5) that uses National Comprehensive Cancer Network Guidelines.¹²⁵ To ensure continuity, a primary nurse will be assigned to each participant. Data collectors will contact IIG by phone within approximately 24 hrs of discharge to collect data (if too ill, re-scheduled within approximately 3 days of discharge) and at approximately the end of each week for 6 wks. The nurse will make a phone visit within approximately 24 hrs of post-surgical discharge to screen participant’s readiness to start exercise. Participants will be deemed ready to start if usual level of severity for key symptoms of pain, nausea, and dyspnea are rated ≤ 4 on an 11-point scale (0-10, 10 = most severe). If participant is ready to exercise, a home visit will be scheduled to start exercise within approximately 4 days of discharge. When severity of a key symptom is rated > 4 , nurse will intervene and contact participant’s surgeon’s office for recommendations. The nurse will repeat this step each day until participant is ready to start exercising. Once participant is ready, nurse will arrange home visit within approximately 3 days. The initial home visit will include connecting Wii to participant’s TV, setting up Wii FitPlus log on password, teaching exercise intervention, and reinforcing CRF self-management education and exercise safety precautions. The nurse will follow-up with phone visit within approximately 24 hrs to answer questions and concerns, make a follow-up home visit at approximately the start of wk 2 of exercise, phone visits at approximately the start of wks 3-6, and additional visits per participant request. During visits, nurse will review IIG participant’s Daily Diary (Appendix A2) with participant and provide PSE-enhancing CRF self-management interventions (Appendix A6). These PSE-enhancing interventions include providing mastery and/or vicarious experiences; social encouragement; and reinterpretation of physical and psychological symptoms to support exercise program to adjust exercise prescription per guidelines. Participant uses Daily Diary to record weekly exercise activity and exercise-related symptoms or issues. IIG participants will be given the option to extend exercise for another 6 wks to study wk 12. Data collection will continue on a weekly basis, culminating with a 6MWT at end of approximately wk 12. Nurse calls will continue weekly to prescribe balance exercises and advance walking prescription 5 mins each week, with goal of achieving minimum 30 min/day. Participants may extend beyond 30 min/day with rate of increase no more than 5 min/day each wk, with participants’ PSE for attaining that duration $\geq 70\%$ on a 0-100% scale (100%=high PSE) (Appendix A1).

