
Section 6.0 Measurement of Effect

As earlier stated following our Specific Aims and Hypothesis, based on existing evidence,⁷²⁻⁷⁵ results of our single-arm pilot (no control group)^{76,77} and two-arm R21 RCT,²³ we expect the benefits of this study to confirm that post-surgical NSCLC patients will find the exercise intervention effective in reducing CRF severity and fatigability (functional capacity). Further, we expect the exercise intervention group will outperform the attention control and wait-list control groups by age for other symptoms' severity; PSE for CRF self-management; PSE for walking; PSE for balance; functional performance; and QOL. We expect the wait-list exercise intervention group's CRF severity and fatigability to improve, but not as significantly as the immediate exercise intervention group. We also expect >50% of the immediate exercise intervention group to extend 6 more wks, with adherence and retention rates of >70% at wk 12, with improved primary and secondary outcomes at wk 12.

Section 7.0 Study Parameters

Measures for Aims 1-3. Aim 1 - Measurement IIG v. ACG and IIG v. WCG Comparisons. Table 3 depicts main study variables and corresponding measures embedded in the concepts of the theoretical framework in Fig 1 (see measures Appendix B1-B9). All measures are administered to all participants using the schedule in Table 3. Participant characteristics as depicted in Table 3 describe the sample. Age is a key biological variable. Given that lung cancer and CRF are significant problems for persons of all ages, and an exercise intervention must be applicable to patients of all ages, study variables will be analyzed for participants by age (< 65 and \geq 65). Also, this study includes men and women as lung cancer is the second most common diagnosed solid tumor with CRF a common symptom for both.¹²⁸ All primary and secondary outcome measures have well established psychometrics, both validity and reliability, with internal consistency scores reported in Table 3 for the cancer

population including use in post-surgical NSCLC.²³⁻²⁴ All measures were used successfully in the R21 RCT without participant complaint about burden. The Karnofsky Performance Scale provides functional impairment classification, universally used in oncology, and is scored from 0% (dead) to 100% (no complaints).¹²⁹

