Perceived Self-Efficacy	Pain Self-Management	The Perceived Self-Efficacy for Pain Self-Management Inventory (6 Items)	Pre & Post-Surgery Weeks 3, 6, 9, 12	Degree of pain self-management. (0.90)

Aim 2 – Measures – WCG Delayed Intervention. At the start of wk 7, WCG will begin the intervention, concluding at wk 12. Aim 1 study variables and measures (Table 3) will be analyzed for Aim 2 for wks 7-12 to compare with the IIG wks 1-6 outcomes.

Aim 3 – Measures – IIG Intervention Sustainability. At the start of wk 7, IIG participants will be given the option to extend the intervention an additional 6 wks. We will measure the extension rate as % participants who elect to extend. Adherence to the intervention will be measured as % participating in the intervention who adhered to prescribed intervention. Weekly adherence will be calculated by taking number of times prescribed intervention was completed divided by total number of interventions prescribed for week. These data are recorded in the Daily Diary and will be confirmed by research staff reviewing recorded data in Wii Fit-Plus. Retention, measured as part of sustainment, will be calculated as % who elected to extend 6 wks who completed final data collection at wk 12. Based on our conceptual definition of sustainability, we will measure the extent to which components of the intervention were rated acceptable for continued use by participant. Acceptability will be measured at end of wk 6 and 12 using a 15-item Acceptability Questionnaire (Appendix B1) using a numeric scale (1 to 6: 6 = agrees strongly) with higher scores indicating greater acceptability of the exercise program. The Questionnaire has a Flesch-Kinkaid 6th grade reading level and was successfully used in our R21 RCT and allows participants to rate how well barriers and facilitators to exercise are addressed. Open-ended questions provide further input.^{23,24} Efficacy will be measured using the same study variables and measures analyzed in Aim 1 (Table 3) for wks 7-12.

Section 8.0 Drug Formulation and Procurement

Not applicable. This study is not a pharmaceutical trial.

Section 9.0 Toxicity and Adverse Event Reporting Guidelines

Study Monitoring

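### Aim 3c treats week-12 improvement in the immediate intervention group as efficacy, although no non-exercising arm is observed after week 6 and the week-12 models cover only participants who chose to extend

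*Combined protocol and SAP*

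**What the plan says.** Hypothesis 3 (Section 1.0) predicts thresholds for extension, adherence and retention, together with an IIG "with improved primary and secondary outcomes at wk 12". Aim 3c names this component efficacy. Section 7.0, Aim 3 measures, repeats the label: "Efficacy will be measured using the same study variables and measures analyzed in Aim 1 (Table 3) for wks 7-12". Neither place says what the outcomes must have improved from, by how much, or compared with whom.

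The design in Section 1.0 has "a wait-list control group (6 wks usual care [wks 1-6] and 6 wks exercise [wks 7-12"]) "or a 6 wk attention control group (wks 1-6"). Figure 8 and Section 5C2b agree: attention-control data are collected weekly for six weeks, and nothing is shown for that arm in weeks 7-12. In the IIG, extension beyond week 6 is optional. For those who extend, Section 5C2 says: "Nurse calls will continue weekly to prescribe balance exercises and advance walking prescription 5 mins each week".

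Section 10.0 gives logistic models for extension, retention and adherence. For continuous 12-week outcomes it gives linear models, with the caveat that they are conditional on electing to extend. No control comparison at week 12 is named.

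**The concern.** An efficacy conclusion needs some view of what would have happened without exercise. At week 6 the trial has this from two randomised arms. At week 12 it has none: one former control is exercising, the other is no longer measured, and the analysed IIG participants have selected themselves.

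Patients recovering from lung surgery may improve without the intervention, and the pilot's usual-care arm (Section 2N) did so on some of the same measures. On the SF-36 physical component: "The UCG improved at a much slower rate, starting at post-surgery level of 32.7 and improving to 38.8 at wk 6 post-study". On symptom interference, usual care "improved to an interference level of 2.9 (SD 2.3) at wk 6", from 4.5 post-surgery. Under the present wording, a change of that kind in the IIG could be reported as sustained efficacy. What is at stake is the attribution of the week-12 result, not the Aim 1 comparison.

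**Working it through.** **1. Who is observed without exercise in weeks 7-12.** IIG: exercising if they extend. Wait-list group: exercising. Attention control: ended at week 6. The answer is nobody, so attribution at week 12 fails for every outcome, whatever the pilot showed. The arithmetic below only asks how easily an uncontrolled test could succeed.

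**2. A figure of the plan's own.** The plan gives no power or sample size for Aim 3. The nearest check is the pilot's within-arm fatigue test in the exercise group: 4.1 (SD 1.9) to 0.7 (SD 0.7), t(36) = 9.9, CI 2.7 to 4.1.
- Standard error = 3.4 / 9.9 = 0.343; CI = 3.4 ± 2.03 × 0.343 = 2.70 to 4.10. This reproduces.
- SD of change = 0.343 × √37 = 2.09.
- Implied pre-post correlation = (1.9² + 0.7² − 2.09²) / (2 × 1.9 × 0.7) ≈ −0.1.

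This is a recoverable pilot correlation with the post-surgery point, so −0.1 is the lower end of the range used; 0.7 is an assumed upper end.

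**3. Pilot usual-care change, post-surgery to week 6 (Section 2N).**
- Symptom severity: 4.9 (SD 1.6) to 3.8 (SD 1.5), a gain of 1.1. The exercise group gained 4.7 − 2.1 = 2.6, so usual care reached 42% of it.
- Interference: 4.5 (SD 2.8) to 2.9 (SD 2.3), a gain of 1.6. Exercise group 3.3 − 0.5 = 2.8; 57%.
- SF-36 physical: 32.7 to 38.8, a gain of 6.1. Exercise group 45.2 − 30.2 = 15.0; 41%. The pilot SD is not given; the population norm of 10 is assumed.

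**4. Probability of a significant within-arm improvement with zero exercise effect.** Assume the IIG changes only as pilot usual care did. SD of change = √(s₁² + s₂² − 2·r·s₁·s₂). Paired t-test, two-sided 5%, noncentral t, n = 30 (half of the 60 in the IIG, the boundary of the extension threshold).

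| Outcome | r = −0.1 | r = 0.3 | r = 0.5 | r = 0.7 |
|---|---|---|---|---|
| Symptom severity | 0.72 | 0.89 | 0.96 | >0.99 |
| Interference | 0.61 | 0.80 | 0.91 | 0.99 |
| SF-36 physical | 0.59 | 0.78 | 0.90 | 0.99 |

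For example, severity at r = 0.5: SD of change 1.55, standardised change 1.1 / 1.55 = 0.71, probability 0.96. With all 60 and r = −0.1 the three values are 0.95, 0.89 and 0.88.

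**5. Outcomes where the pilot does not show recovery.**
- Fatigability (primary here): usual-care walk-test fatigue rose from 1.5 pre-surgery to 3.1 and distance fell by 21%. The chance of a false improvement is essentially zero.
- Symptom count rose from 6.6 to 7.4, and self-efficacy for fatigue fell from 7.6 to 6.9. The chance is below 0.003 at n = 30 over the same correlations.
- SF-36 mental: dropped after surgery, then flat (47.4 and 47).
- Fatigue severity (primary): 4.0 (SD 2.0) at week 6. The usual-care post-surgery mean is only in a figure not shown. If it was 4.1, the exercise group's value, the chance is about 0.04 to 0.07 over n = 31 to 60. If it was 4.5, it is 0.15 to 0.71. Both starting values are assumptions, as is a starting SD of 1.9.

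**The case against.** The strongest reply is that Hypothesis 3 is conjunctive. It also requires acceptability, extension above 50%, adherence and retention above 70%, and improvement in primary as well as secondary outcomes. A reader might infer from the pilot that natural recovery alone could confirm the hypothesis. The documents do not support that: the three improving outcomes are all secondary, a primary outcome worsened under usual care, and Section 2B cites persistent or worsening fatigue after surgery. This part of the reply stands.

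It is also fair that the plan specifies no within-arm paired test. Section 10.0 adjusts for baseline fatigue, and baseline is pre-surgery; measuring from post-surgery favours apparent recovery. The 6-minute walk has no post-surgery assessment, so that reference could not serve fatigability. The table is therefore an illustration, conditional on one reading of 'improved'. But adjusting for baseline does not define what counts as improved, and it supplies no control, so the gap remains.

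Two further readings go too far. Section 7.0 says "All measures are administered to all participants using the schedule in Table 3", and Table 3 runs to week 12, which might suggest attention-control data at week 12. That sentence sits under the Aim 1 measures, Table 3 also lists Wii exercise that this arm does not do, and Figure 8 and Section 5C2b give the arm-specific schedule ending at week 6. Second, one might say that continued nurse prescribing contradicts the definition of sustainability in Section 2M, as use beyond initial implementation. Since the intervention is described as six weeks long, an elective extension can be read as meeting that definition. This is a matter of interpretation.

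**Conclusion.** The concern holds in a limited form. The design cannot support an efficacy conclusion at week 12 for any outcome, because no non-exercising arm is observed after week 6 and the models are restricted to self-selected extenders. This follows from the design alone.

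On symptom severity, interference and SF-36 physical, usual-care recovery of the pilot's size would make an uncontrolled test significant with probability 0.59 to above 0.99 at n = 30. That range assumes a test from post-surgery, correlation −0.1 to 0.7, an SF-36 SD of 10, and the six-week pilot change carried to week 12; there are no untreated data for weeks 7-12. For fatigability, symptom count, self-efficacy for fatigue and the mental component the pilot shows no such recovery, and for fatigue severity it cannot be settled from the text. Natural recovery would therefore not confirm the whole of Hypothesis 3. Aim 1 keeps its randomised controls at week 6 and is unaffected. The correction should be made because it changes what the trial may claim about sustainability.

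**What to change.** - In Aim 3c, Hypothesis 3 and the Aim 3 paragraph of Section 7.0, replace 'efficacy' and 'improved' with within-group maintenance under continued nurse-supported exercise.
- In Section 10.0, specify the mean week-12 minus week-6 change with its 95% CI for the BFI and fatigability among IIG participants with week-12 data. Both are scheduled at both times in Table 3. State that the result describes extenders.
- Add a sensitivity analysis for all randomised to the IIG, using the imputation and inverse-probability weighting already mentioned in Section 10.0. Week-12 data on non-extenders are not clearly provided for, so this analysis will rest on assumptions about them, which should be stated.
- State that no causal claim is made at week 12 and that randomised efficacy rests on Aim 1 at week 6.
- Minor: align the general sentence in Section 7.0 with Figure 8 and Section 5C2b on when attention-control measurement ends.

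The cost is wording, one contrast on data already scheduled and one sensitivity analysis. No visits or participants are added. The price is a more modest Aim 3c claim.
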